Dose-levels	ABI-009 in mg/m ²												
-2	1												
-1	2.5												
1	5												
2	10												
3	20												

	
then a new cohort of 3 participants at the next higher dose level can be enrolled. If 2/6 participants at dose level 1 experience a DLT, then that cohort will be closed to further enrollment and 3 participants will be enrolled at the next lower dose level, and so on. The MTD is the highest dose level in which ≤ 1 participant has a DLT.
 
Once the MTD has been determined, the MTD cohort will be opened for an additional 6 participants. These participants will adhere to the identical protocol of the rest of their cohort.
 
Product will be administered IV every seven days for three weeks.

CONTROL PRODUCT, DOSE AND ROUTE OF ADMINISTRATION	
There is no control product for this study. Participants will serve as their own controls by continuing their pre-existing AED regimen for 1 month after enrollment prior to starting dosing with ABI-009. In order to proceed with drug administration participants will have to have had >8 seizures in 30 days without 2 consecutive weeks of seizure freedom.

CONCOMITANT MEDICATIONS	
Allowed: Standard therapy for epilepsy is allowed except for treatments noted in the prohibited medications section below. Pre-existing AEDs must not be titrated while participants are enrolled in the study, unless the dose change is solely to address subtherapeutic levels as determined by the treating neurologist. Rescue medication is allowed for prolonged seizure event or cluster of seizures.
 
Prohibited: The following medication changes are prohibited during participation in the trial, and as such will be considered a protocol violation:
 
 • Any changes in dosage of AED regimen, unless solely to address subtherapeutic levels of AEDs as determined by the treating neurologist. • Any additions or removal of AEDs to the participant's AED regimen during participation unless medically necessary and discussed with investigator
PRIMARY ENDPOINT	
Safety:
 
DLT and MTD
 
Incidence of adverse events and clinically significant abnormal lab values
 
Tolerability:
 
Number of participants withdrawn from study
 
Adherence to prescribed ABI-009 regimen
 
Columbia-Suicide Severity Rating Scale (C-SSRS) serious suicidal ideation score stays below a 4 rating.

SECONDARY	
Efficacy:

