ENDPOINTS	
Seizure frequency Percentage reduction in seizure frequency Median percentage reduction in seizure frequency Response rate Frequency of seizure-free days Seizure-free rate Rapamycin blood level–response relationship
 
Other:
 
Quality of life and behavioral index Determine weekly whole blood rapamycin trough levels for three consecutive weeks

STATISTICS Primary Analysis Plan	
Analysis of Primary Endpoints
 
The number of SAEs and AEs will be summarized for each dosing group as follows: (i) The proportion of participants with at least one (S)AE, (ii) The average number of (S)AEs per participant, and (iii) The rate of (S)AEs per participant week of follow-up. Histograms showing the frequency of the number of (S)AEs in each dosing group will be included. Rates of (S)AEs by System Organ Class (SOC) will be presented by treatment group. Poisson regression modeling for count data will be used to derive rate ratios and 95% CIs for each SOC.
 
Safety lab data at each study visit and changes from baseline will be summarized by dosing group. In addition, the following clinical laboratory summaries will be presented by dosing group: (i) the incidence of clinically significant abnormalities at each study visit; and (ii) tables summarizing the frequencies of participants below, within, and above the normal reference ranges at baseline and end of study; and (iii) tables displaying baseline to end of study shifts in each laboratory value (shifts between below, within or above normal range).
 
The number of hospitalization events and proportion of participants hospitalized from baseline to final day of study will be summarized and compared by treatment group. Poisson regression modeling will be used to derive rate ratios and 95% CIs.
 
Study compliance will be assessed via compliance with scheduled weekly infusions.
 
Analysis of Secondary Endpoints
 
Efficacy is defined as the change in seizure frequency between baseline and follow-up, expressed as percentage reduction in seizure rate (reduction in seizure frequency from baseline, calculated as (Baseline frequency [seizures/week] – frequency at follow-up

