15 STATISTICAL METHODS AND CONSIDERATIONS

15.1 General Considerations

Prior to the analysis of the final study data, a detailed Statistical Analysis Plan (SAP) will be written, describing all analyses that will be performed. The SAP will contain any modifications to the analysis plan described below.

For the purposes of analyses, baseline period will be defined as Days 0-30. Except where otherwise noted, comparisons of continuous variables between pre and post treatment periods will utilize t-tests or linear regression, test of proportions and analysis of count data using Poisson regression. Except where otherwise noted, all tests will be two-sided and statistical significance will be determined at the 0.05 level. Missing data methods for the primary and key secondary endpoints will be described in the SAP. No adjustment for multiple comparisons will be made.

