15.1.1 Data Sets Analyzed

All analyses will be performed using a pre-/post-treatment comparison within participants. The primary safety/tolerability analysis and key secondary endpoints will be repeated in the per-protocol population, which is defined as participants having completed >80% of study drug doses and have incurred no major protocol violations. The per-protocol analyses will analyze participants according to the treatment they received.

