15.3 Analysis of Primary Endpoint - Safety Endpoints

All reported treatment emergent SAEs and AEs will be coded using MedDRA and grouped by body system. Treatment emergent AEs are defined as AEs presenting post study treatment initiation. SAEs and AEs will be tabulated using standard coding terms sorted by body system. The incidence of AEs in each treatment arm will be tabulated by seriousness, severity, and relationship to study drug. If an AE is reported more than once during the study period for a given participant, the greatest severity and the worst-case relationship will be presented in tables.

The number of SAEs and AEs will be summarized as follows: (i) The proportion of participants with at least one (S)AE, (ii) The average number of (S)AEs per participant, and (iii) The rate of (S)AEs per participant week of follow-up. Histograms showing the frequency of the number of (S)AEs in each treatment group will be included. Rates of (S)AEs by System Organ Class (SOC) will be presented by treatment group. Poisson regression modeling will be used to derive rate ratios and 95% CIs for each SOC.

Safety lab data at each study visit and changes from baseline will be summarized by treatment group. In addition, the following clinical laboratory summaries will be presented by treatment group: (i) the incidence of clinically significant abnormalities at each study visit; and (ii) tables summarizing the frequencies of participants below, within, and above the normal reference ranges at baseline and end of study; and (iii) tables displaying baseline to end of study shifts in each laboratory value (shifts between below, within or above normal range).

The number of hospitalization events and proportion of participants hospitalized will be summarized and compared by treatment group. Poisson regression modeling will be used to derive rate ratios and 95% CIs to compare hospitalization rates between treatment groups.

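### The synopsis counts hospitalisations for the dose-group comparison from baseline, so about 20–22% of the nominal window precedes any infusion; section 15.3 gives no window at all

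*Combined protocol and SAP*

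**What the plan says.** The synopsis, under Analysis of Primary Endpoints, covers the number of hospitalisation events and states that the "proportion of participants hospitalized from baseline to final day of study will be summarized and compared by treatment group". Poisson regression then supplies rate ratios with 95% confidence intervals. There is no control arm, so the treatment groups are the dose groups.

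Section 15.3 repeats the analysis without a start or end: "The number of hospitalization events and proportion of participants hospitalized will be summarized and compared by treatment group". It uses Poisson regression to "derive rate ratios and 95% CIs to compare hospitalization rates between treatment groups". The same section opens by restricting the coded AE and SAE tables to treatment-emergent events: "Treatment emergent AEs are defined as AEs presenting post study treatment initiation". It does not extend that restriction to hospitalisations.

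Other provisions bear on the start of the count:

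- Section 15.1: "For the purposes of analyses, baseline period will be defined as Days 0-30".
- Synopsis, Control Product: participants act as their own controls by "continuing their pre-existing AED regimen for 1 month after enrollment prior to starting dosing with ABI-009".
- Section 15.1.1: "All analyses will be performed using a pre-/post-treatment comparison within participants".
- Sections 11.2 and 11.2.1: an inpatient hospitalisation is an SAE, and SAEs are collected from consent, so admissions in the baseline month will be in the database.

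**The concern.** A between-dose comparison of hospitalisation should count events and time in which the dose could have acted. Read with the only analysis definition of baseline, the synopsis window begins about a month before the first infusion. An admission in that month cannot be caused by ABI-009, yet it would be tallied against the dose level the participant later received.

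Such admissions are plausible: the participants have refractory epilepsy, and more than 8 seizures in 30 days are required before dosing. Two things follow. The count and the proportion hospitalised in each dose group include events unrelated to dose. The added drug-free person-time also moves any real dose difference toward no difference, which is the unwelcome direction for a safety comparison. Because section 15.3 states no window, two analysts could follow the protocol and produce different tables.

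**Working it through.** **Length of the window.** Section 4.1 states participation of up to 18 weeks, made up of 4, 3 and 12 weeks. These sum to 4 + 3 + 12 = 19, not 18. Counting follow-up from the third infusion, two weeks after the first, gives 4 + 2 + 12 = 18, which matches. The visit schedule (section 10, Appendix 1) puts the end of baseline at Day 30, allows dose 1 on that day, and sets the last visit 90 days after dosing. That gives 30 + 14 + 90 = 134 days, of which 104 follow the first infusion.

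**Pre-infusion share** = baseline length / total window.

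| Reading | Share |
|---|---|
| 4 of 18 weeks | 22.2% |
| 4 of 19 weeks | 21.1% |
| 30 of 134 days | 22.4% |
| 30 of 30 + 21 + 90 = 141 days | 21.3% |
| 1 of about 5 months (synopsis) | 20.0% |

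With the visit windows at their extremes and dose 1 on the day of Visit 2, the range is 28/(28 + 14 + 97) = 20.1% to 35/(35 + 14 + 83) = 26.5%.

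**Effect on the rate ratio.** Assume a constant background rate common to all groups, a comparison group that stays at background, and an effect R that lasts all 104 post-dose days. The observed ratio is (30 + 104R)/134:

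- R = 1.5: 186/134 = 1.39
- R = 2: 238/134 = 1.78
- R = 3: 342/134 = 2.55

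**If the effect is short.** Section 1.10 gives a half-life of about 60 hours (at 45–150 mg/m²). As an illustration, take an effect lasting the 14 dosing days plus five half-lives, about 26 days in all. With R = 2, counting from the first infusion gives (26 × 2 + 78)/104 = 1.25. Counting from Day 0 gives (30 + 26 × 2 + 78)/134 = 160/134 = 1.19. Most of the dilution then comes from the long follow-up and would remain after the fix.

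**Effect on the proportion.** In a cohort of 3, one pre-infusion admission moves the proportion hospitalised from 0/3 to 1/3, or 33%. The documents give no admission rate. Assume a chance p of 2% to 20% per participant in the baseline month. The chance of at least one such admission, 1 − (1 − p)^n, is 6% to 49% for n = 3 and 11% to 74% for n = 6.

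**The case against.** The best counter-argument is that baseline may mean a visit rather than a period. Sections 3.2 and 5.2 place the QOLCE and NCBRF at baseline, and sections 9.1.9 and 9.1.10 give them at the end of the baseline month, on a visit that may also be dose 1. On that usage the pre-infusion share is about 0%. This reading is possible, but section 15.1 defines the period for analysis as Days 0–30 and nothing ties the hospitalisation count to the later visit. The start point still has to be stated.

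It is also fair to say that little depends on this table. Escalation and the MTD rest on DLTs (sections 4.1 and 8.5), the DSMB reviews AEs before each escalation (section 14), and hospitalisation is not separately listed as a primary endpoint in section 5.1. Precision will be poor: an illustrative 4 versus 2 admissions with equal person-time gives a ratio of 2 with a 95% interval of exp(ln 2 ± 1.96 × √(1/4 + 1/2)), about 0.37 to 10.9. A shift to 1.78 is small beside that. These points limit the importance of the problem but give no reason to include drug-free time.

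Three stronger inferences are not supported:

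- A reader might infer that every group's hospitalisation rate is inflated. Under a constant background the baseline month adds person-time as well as events. An unaffected group's rate is unchanged and an affected group's rate falls; only counts and proportions rise.
- A reader might infer that the plan contains two directly conflicting harm tables. The window appears only in the synopsis, whose AE summary has no treatment-emergent restriction; that restriction appears only in section 15.3, whose hospitalisation paragraph has no window. This is a difference between synopsis and body to be reconciled.
- A reader might infer that the within-participant control has been abandoned. Section 15.1.1 keeps a pre/post comparison for all analyses, although section 15.3 does not spell it out for hospitalisation.

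**Conclusion.** The point holds in a limited form. Following the synopsis with the section 15.1 definition of baseline puts about 20–22% drug-free time, nominally 30 of 134 days, into a between-dose safety comparison listed under the primary analyses, and no text removes it. The dilution of a true ratio of 2 to 1.78 rests on three assumptions: a common constant background, a comparison group that stays at background although every cohort is dosed, and an effect that lasts the whole post-dose window. With a short-lived effect, the choice of start point changes little in the ratio. The more visible risk is in small cohorts, where a single pre-infusion admission changes the proportion hospitalised substantially and can distort the comparison in either direction. The effect is modest and no dose decision depends on it, but the start of the count is unclear and easily settled before the detailed SAP promised in section 15.1 is written.

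**What to change.** In both the synopsis and section 15.3, state that hospitalisation counts, proportions hospitalised and the person-time offset for the dose-group comparison run from the first infusion to the final study day. This aligns them with the treatment-emergent rule already in section 15.3. Report Days 0–30 admissions separately, with their own person-time, and set that rate beside the post-infusion rate as the within-participant comparator that section 15.1.1 calls for.

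The change is to wording only. Section 9.1.14 already has AE start and end dates recorded on the CRF, so no new data item is evident. The downside is slightly fewer events in an already sparse table.

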1 BACKGROUND

1.1 Intractable epilepsy in children

Unlike adults, the primary objective of epilepsy surgery in the pediatric population is to avoid the adverse consequences of uncontrolled epilepsy, particularly with regards to cognitive and developmental outcomes [4]. Additionally, aggressive seizure control in young children is mandatory to avoid the development of the epileptic encephalopathy [5]. It is this desire to avoid the untoward sequelae of intractable epilepsy in developing children that underscores the necessity for early diagnosis and referral to a pediatric epilepsy surgery center.

A critical point is that the diagnosis of therapy-resistant (i.e., intractable) epilepsy can be made early without an exhaustive trial of antiepileptic medications. This concept has been borne out of epidemiological studies done early last decade. Among children in the general population, the incidence of epilepsy has been estimated at five cases per 10000 per year [6, 7]. Of these, from 23% to 33% will become pharmacoresistant [8-10]. Pharmacoresistant epilepsy is usually defined as one or more seizures per month that persist after trying more than two antiepilepsy drugs (AEDs) [11]. Pharmacoresistance is best predicted by the response to AEDs. Once a patient has failed two to four AEDs, the chances that additional medications will stop the seizures are less than 5% [12]. If there is an associated lesion on MRI, the chance that additional medications will stop the seizures is near zero [13, 14].

Epilepsy syndrome classification predicts response to medical therapy. Nearly all children with genetic/idiopathic epilepsy experience near-optimal seizure control with medication. Of these, approximately 59% experience remission at one year and 40% of children have less than one seizure a month. Thus, 99% of children with genetic epilepsy have near-complete seizure control. Approximately 92% of children with cryptogenic/unknown epilepsy achieve near-optimal seizure control at two years. Remission rates for metabolic/structural epilepsy, on the other hand, are not as high with medical therapy with about 50% uncontrolled on AEDs. Many children considered for epilepsy surgery have metabolic/structural seizures. Furthermore, the development of new AEDs has not significantly impacted seizure control in children of this latter group [15].

Risk factors, such as mental retardation, perinatal anoxia, a history of neonatal convulsions, a history of status epilepticus, and symptomatic etiology increase the risk of refractory epilepsy in children [16]. Younger age at seizure onset and frequent seizures (more than once per month) are also independent risk factors for the development of treatment resistance. Furthermore, high initial seizure frequency and focal EEG findings correlate with intractability.

Suboptimal seizure control in infants, children, and adolescents poses serious neurodevelopmental consequences, spanning cognitive, behavioral, and psychosocial domains. Intellectual dysfunction (IQ <79) can be detected in 57% of children with uncontrolled unilateral temporal lobe epilepsy [17]. Independent of etiology, intractable seizures during the first 24 months of life is a significant risk factor for mental retardation [18]. Intellectual deterioration is particularly rampant when seizures occur daily. When uncontrolled unilateral temporal lobe epilepsy begins in the first 12 months of life, the incidence of intellectual impairment is approximately 83%. Inadequately controlled infantile spasms may result in severe impairments of cognition, language, social skills, and communication abilities that appear to be clinically similar to autism [19].

Beyond cognition, suboptimal seizure control may result in poor psychosocial outcomes compared with patients whose epilepsy is controlled [20]. Psychosocial deficiencies manifest as lower rates of high school completion, employment, marriage, and overall socioeconomic productivity. Early surgical intervention for intractable seizures results in improved IQ scores and developmental indices [5, 21-25].

Early intervention to control seizure frequency is also critical to reducing seizure-related morbidity and mortality. Compared to children without disease, children with refractory epilepsy are at risk of higher rates of morbidity and death [26-28]. The mortality risk of uncontrolled epilepsy is approximately 0.5% per year and accumulates over the child's lifetime. Examples of the seizure-related mortality include sudden unexplained death due to epilepsy (SUDEP), aspiration pneumonia, trauma, accidents, drowning, and status epilepticus. Importantly, SUDEP risk does not change with medically controlled seizures, but is only reduced in the population made seizure-free.

In order to reduce the risk of developmental decline and decrease seizure-related morbidity and mortality, surgical therapy should be considered as a therapeutic option in the management of some therapy-resistant children. Furthermore, psychosocial function and quality of life indices may benefit greatly from seizure control.

1.2 Clinical characteristics of pediatric epilepsy surgery patients

The general clinical features of pediatric epilepsy surgery patients are those associated with a high risk of inducing an epileptic encephalopathy. This is best illustrated from the results of an international survey of pediatric epilepsy surgery centers for the calendar year 2004 [29]. For example, age at seizure onset is two years or less in 83% and seizures frequency is daily or greater in 65% of cases. Of note, fewer than 32% of children receive their epilepsy surgery within two years of onset. Thus, many children are exposed to an epilepsy duration that is associated with the poorest developmental outcomes.

Etiologies are often quite variable in patients undergoing pediatric epilepsy neurosurgery. Cortical dysplasia (CD), a congenital structural aberration consisting of cortical dyslamination and columnar disorganization, is the most commonly encountered substrate in pediatric epilepsy surgery. Cortical dysplasia can be graded as severe or mild [30, 31]. While milder forms of CD solely involve defects in lamination, severe cortical dysplasia consists of cortical dyslamination with the addition of abnormal cytomegalic neurons and balloon cells in the cortex and subcortical white matter [32, 33]. Severe CD is more likely to present at younger ages, have higher seizure frequencies, and be extratemporal [34]. Though CD is most often detected using conventional structural MRI, abnormalities may be subtle or undetectable. In addition, scalp EEG may be non-localized from 23% to 50% of cases. For this reason, adjunctive neuroimaging such as FDG-PET, MEG, and ictal-SPECT may be utilized. FDG-PET, in particular, is positive in 75 to 90% of CD cases [35]. Focal CD is most often found in the frontal and temporal lobes, though larger lesions may involve multiple lobes or a cerebral hemisphere. In our experience, children with early-onset epilepsy tend to have larger dysplastic lesions with more severe CD histopathology.

The second most common substrate found in pediatric epilepsy surgery patients is low-grade neoplastic tumors, such as gangliogliomas and dysembryoplastic neuroepithelial tumors (DNETs). Seizures are the first clinical presentation in about 80% of patients with low-grade

tumors [36, 37]. DNETs may also be found in association with regions of cortical dysplasia. Fortunately, high seizure remission rates result from complete resection of these tumors [38]. Other structural abnormalities leading to pediatric epilepsy surgery may result from perinatal infarcts or infections such as bacterial or viral encephalitides [39]. While hippocampal sclerosis is the most common etiology in adult epilepsy surgery patients, it is less frequent in children.

Other etiologies are much less frequent in pediatric epilepsy surgery patients. In Sturge-Weber, for example, suboptimal seizure control may lead to developmental delay and progressive hemiparesis. For this reason, children may require focal or hemispheric resections to prevent developmental decline [40]. Tuberous sclerosis complex (TSC), a phakomatosis that results in hamartomatous lesions throughout the body, is another fairly rare condition referred for epilepsy surgery consideration. In TSC patients, seizures may be focal or multifocal, are often treatment-resistant, and may impair neurocognitive development [41-43]. Even though in many of these cases there are several tubers as well as multifocal EEG abnormalities, optimal seizure control may result from resection of the epileptogenic cortical tuber(s) [44-46].

Rasmussen's syndrome, hypothalamic hamartoma, and hemimegalencephaly are other less-frequently encountered substrates in pediatric epilepsy surgery. Rasmussen's syndrome is a disease of unknown cause where progressive involvement of one hemisphere leads to hemiparesis and intractable seizures [47]. While steroids, immunoglobulins, and plasmapheresis provide temporary relief, hemispherectomy is the only known effective treatment. Laundau-Kleffner syndrome, an epileptic aphasia that associated with severe developmental regression and intractable seizures, may respond to surgical intervention [48]. Hemimegalencephaly is a phenomenon where one hemisphere is hypertrophied and contains abnormal and dysplastic glioneuronal proliferation [49]. Children with hemimegalencephaly have unilateral or bilateral EEG abnormalities often with hysparrhythmia or suppression bursts. These children also present with macrocrania, mental retardation, and contralateral paresis. Hemispherectomy provides the best chances for seizure control and normalization of psychomotor development velocity [50].

